# Listing 16.2.3 Inclusion/Exclusion Criteria not Met Safety Population

Subject ID	Criteria Not Met	Description of Criteria
xxxxxx	INCXX	xxxxxxxxxxxxxxxxx
XXXXXXX	EXCLXX	xxxxxxxxxxxxxxxxx

Protocol Number: NI-AC303

Listing 16.2.4.1
Demographics
Safety Population

Subject ID	Study Center	Date of Birth	Age (years)	Gender	Ethnicity	Race
xxxxxxx	xxxxxxx	DDMMMYYYY	XX.X	Male	Not Hispanic or Latino	xxxxxx
xxxxxxx	xxxxxx	DDMMMYYYY	xx.x	Female	Not Hispanic or Latino	xxxxx
xxxxxxx	xxxxxx	DDMMMYYYY	XX.X	Female	Not Hispanic or Latino	Other: xxxxxx

Note(s): Age is calculated as the interval between date of birth and date of baseline visit from the previous study (NI-AC301 or NI-AC302).

s<nnn>xxxx yyyymmddthh:mm

Protocol Number: NI-AC303

Listing 16.2.4.2 Medical History Safety Population

Subject ID	SOC / Preferred Term / Verbatim Term	Onset / End
xxxxxx	Xxxxxxxx / Xxxxxxxx / xxxxxxxx	DDMMYYYY / DDMMYYYY
xxxxxxx	Xxxxxxx / Xxxxxxxx / xxxxxxxx	DDMMYYYY / Ongoing

s<nnn>xxxx yyyymmddthh:mm

Protocol Number: NI-AC303

# Listing 16.2.4.3 Child Bearing Potential and Pregnancy Test Results Safety Population (Females only)

Subject ID	Of Child- Bearing Potential?	If no, why?	If Yes, Method of Birth Control	Visit	Collection Date / Day	Pregnancy Test Result or Reason Not Done	
XXXXXXX	Yes No	XXXXXXXXXXX	xxxxxxxxx	Baseline Baseline	DDMMMYYYY /XX DDMMMYYYY /XX	Negative Negative	

Note(s): Day = Day relative to the date of first day of LTS. s<nnn>xxxx yyyymmddthh:mm

Novan Inc
Protocol Number: NI-AC303

Safety Population

Listing 16.2.4.4
Physical Exam

Subject ID	Visit	Date	Body System	Evaluation	Abnormality
XXXXXXX	Baseline	DDMMMYYYY	General Appearance Respiratory Cardiovascular Other: XXXXXXXX	Normal Normal Normal ANCS	xxxxxxxxxxxxxxxxxxxxxxxxxxxxxxxxxxxxxxx
	Week 40\ET	DDMMMYYYY	General Appearance Respiratory Cardiovascular	ACS Normal	xxxxxxxxxxxxxxx
	Etc.		cararovascurar	NOTHIAL	
XXXXXXX	Baseline	DDMMMYYYY	General Appearance Respiratory	Normal Normal	

Note(s):ANCS = Abnormal, Not clinically significant; ACS = Abnormal, Clinically Significant. If a finding was determined to be clinically significant, it is also reported as an adverse event, or, if it occurred prior to study start, it is reported in medical history. s<nnn>xxxx yyyymmddthh:mm

Protocol Number: NI-AC303

Listing 16.2.5
Study Drug Management
Safety Population

Subject			Was Pump			Was previous	
ID	Visit	Date/ Day	dispensed?	If yes,	Pump number(s)	pump returned?	If no. Reason why:
		,					
XXXXXXX	Baseline	DDMMMYYYY/xx	Yes	XXXXXX			
	Week 4	DDMMMYYYY/xx	No			No	XXXXXXXXX
	Week 12	DDMMMYYYY/xx	Yes	XXXXXX,	XXXXX		
	Week 24	DDMMMYYYY/xx	Yes	XXXXXX,	XXXXX, XXXXX		
	Week 36	DDMMMYYYY/xx	Yes	XXXXXX			
	Week 40	DDMMMYYYY/xx	Yes	XXXXXX			
Xxxxxxx	Baseline	DDMMMYYYY/xx	Yes	XXXXXX			
	Week 4	DDMMMYYYY/xx	Yes	XXXXXX			
	Week 12	DDMMMYYYY/xx	Yes	XXXXXX		Yes	
	Week 24	DDMMMYYYY/xx	Yes	XXXXXX			
	Week 36	DDMMMYYYY/xx	Yes	XXXXXX			
	Week 40	DDMMMYYYY/xx	Yes	XXXXXX			
xxxxxxx	Baseline	DDMMMYYYY/xx	Yes	XXXXXX			
***************************************	Week 4	DDMMMYYYY/xx	Yes	XXXXXX		Yes	
	Week 12	DDMMMYYYY/xx	Yes	XXXXXX		105	
	Week 24	DDMMMYYYY/xx	No				
	Week 36	DDMMMYYYY/xx	Yes	XXXXXX			
	Week 40	DDMMMYYYY/xx	Yes	XXXXXX			
	WCCI 40	DDIMMITTIT/ AA	100	2121212121			

Note(s): Day = Day relative to the date of first day of LTS.

Protocol Number: NI-AC303

Listing 16.2.6
Extent and Duration of Exposure
Safety Population

	Visit		Duration of Exposure (days)	Doses re Reported		Extent of			Areas of Application		
Subject ID		Date			Days of Exposure	Exposure (grams)	Face	Upper Back	Upper Chest	Shoulders	Other:
	57 - 1 4		77777	373737	77777	171717		**			
XXXXXXX	Week 4	DDMMMYYYY	XXX	XXX	XXX	XXX	X	X			
	Week 12	DDMMMYYYY	XXX	XXX	XXX	XXX		X		X	
	Week 24	DDMMMYYYY	XXX	XXX	XXX	XXX			X	X	
	Week 36	DDMMMYYYY	UNK	UNK	UNK	UNK				X	Neck and Jawline
	Week 40	DDMMMYYYY	XXX	XXX	XXX	XXX					
	Overall		XXX	UNK	UNK	UNK					
										x	xxxxxxxxx
Xxxxxx	Week 4	DDMMMYYYY	XXX	XXX	XXX	XXX					
	Week 12	DDMMMYYYY	XXX	XXX	XXX	XXX					
	Week 24	DDMMMYYYY	XXX	XXX	XXX	XXX					
	Week 36	DDMMMYYYY	XXX	XXX	XXX	XXX					
	Week 40	DDMMMYYYY	XXX	XXX	XXX	XXX					
	Overall		XXX	XXX	XXX	XXX					

#### Note(s):

Duration of Exposure = (Date of next drug dispensation or if last dispensataion, date of last dose) - Date of Drug Dispensation + 1 day. Overall is based on the date of first dose of study drug, which could be from the previous study (NI-AC301 or NI-AC302).

Days of Exposure = Duration of exposure minus the number of days that the subject reported not taking study medication. Extent of Exposure: Each application is equal to 0.9 g. Extent of exposure is estimated as the sum of application areas (face only=1, face and chest=2, etc) times the number of days of application to those areas times 0.9g. If the other specification is jaw or neckline, it is assumed that the same pump stroke used to apply drug to face is being used for the jaw and/or neckline application. For subjects randomized to SB204 in the previous studies, drug was only applied to the face so for the days of exposure from the previous studies, it will be assumed that there is only one area of application, i.e. the face.

UNK = Unknown: For subjects who are lost-to-follow-up or who did not return diaries but reported an unknown number of missed doses, duration of exposure and days of exposure for that visit interval are defined as unknown. Overall duration will be defined as above; days of exposure will remain unknown.

Protocol Number: NI-AC303

Listing 16.2.7.1.1

Lesion Counts (Face Only): Total Inflammatory and Non-Inflammatory Lesions
Safety Population

				_	Infl	Lammatory Le	sions	Non-Ir	nflammatory :	Lesions
Previous	Subject			Counter's		Absolute Change from	Percent Change from		Absolute Change from	Percent Change from
Study	ID	Visit	Date	Initials	Count	Baseline	Baseline	Count	Baseline	Baselin
		Baseline	DDMMMYYYY	XXXX	XX			XX		
XXXXXX	XXXXXXX	Week 4	DDMMMYYYY	XXXX	XX	XX	XX	XX	XX	XX
					XX	XX	XX	XX	XX	XX
		Week 12	DDMMMYYYY	XXXX						
		Week 24	DDMMMYYYY	XXXX	XX	XX	XX	XX	XX	XX
		Week 36	DDMMMYYYY	XXXX	XX	XX	XX	XX	XX	XX
		Week 40	DDMMMYYYY	XXXX	XX	XX	XX	XX	XX	XX
xxxxxx	xxxxxxx	Baseline	DDMMMYYYY	XXXX	XX			XX		
		Week 4	DDMMMYYYY	XXXX	XX	XX	XX	XX	XX	XX
		Week 12	DDMMMYYYY	XXXX	XX	XX	XX	XX	XX	XX
		Week 24	DDMMMYYYY	XXXX	XX	XX	XX	XX	XX	XX
		Week 36	DDMMMYYYY	XXXX	XX	XX	XX	XX	XX	XX
		Week 40	DDMMMYYYY	XXXX	XX	XX	XX	XX	XX	XX

Note: Inflammatory Lesions includes: papules/pustules + nodules/cysts.s<nnn>xxxx yyyymmddthh:mm

Novan Inc
Protocol Number: NI-AC303

Listing 16.2.7.1.2

Lesion Counts (Face Only): Papules, Pustules, Nodules, and Cysts

Safety Population

Previous Study	Subject ID	Visit	Date	Counter's Initials	Papules/Pustules	Nodules/Cyst:
rievieus seud i	542,555 12	11010	2400	111101010	rapares, rassares	reduites, equal
xxxxxx	xxxxxxx	Baseline	DDMMMYYYY	XXXX	XXX	XXX
		Week 4	DDMMMYYYY	XXXX	XXX	XXX
		Week 12	DDMMMYYYY	XXXX	XXX	XXX
		Week 24	DDMMMYYYY	XXXX	XXX	XXX
		Week 36	DDMMMYYYY	XXXX	XXX	XXX
		Week 40	DDMMMYYYY	XXXX	XXX	XXX
xxxxxx	xxxxxx	Baseline	DDMMMYYYY	XXXX	XXX	XXX
		Week 4	DDMMMYYYY	XXXX	XXX	XXX
		Week 12	DDMMMYYYY	XXXX	XXX	XXX
		Week 24	DDMMMYYYY	XXXX	XXX	XXX
		Week 36	DDMMMYYYY	XXXX	XXX	XXX
		Week 40	DDMMMYYYY	XXXX	XXX	XXX

Protocol Number: NI-AC303

Listing 16.2.7.3 Cutaneous Tolerability Safety Population

Previous Study	Subject ID	Visit	Date	Erythema	Scaling	Dryness	Pruritus	Burning/ Stinging
xxxxxxx	xxxxxxx	Baseline	DDMMMYYYY	Mild	Mild	Moderate	None	None
		Week 4	DDMMMYYYY	Mild	Mild	Moderate	None	None
		Week 12	DDMMMYYYY	Mild	Mild	Moderate	None	None
		Week 24	DDMMMYYYY	Mild	Mild	Moderate	None	None
		Week 36	DDMMMYYYY	Mild	Mild	Moderate	None	None
		Week 40	DDMMMYYYY	Mild	Mild	Moderate	None	None
xxxxxxx	xxxxxxx	Baseline	DDMMMYYYY	Mild	Mild	Moderate	None	None
		Week 4	DDMMMYYYY	Mild	Mild	Moderate	None	None
		Week 12	DDMMMYYYY	Mild	Mild	Moderate	None	None
		Week 24	DDMMMYYYY	Mild	Mild	Moderate	None	None
		Week 36	DDMMMYYYY	Mild	Mild	Moderate	None	None
		Week 40	DDMMMYYYY	Mild	Mild	Moderate	None	None

Note(s): 0 = None, 1 = Mild, 2=Moderate, 3 = Severe. s<nnn>xxxx yyyymmddthh:mm

Protocol Number: NI-AC303

Listing 16.2.7.4 Vital Signs Safety Population

Previous Study	Subject ID	Visit	Date/ Day	Systolic BP (mmHg)	Diastolic BP (mmHg)	Pulse (bpm)	Evaluation	If Abnormal and Clinically Significant, provide MH or AE term
xxxxxx	xxxxxx	Baseline	DDMMMYYYY/xx	xxx	xxx	XXX	Normal	
		Week 4	DDMMMYYYY/xx	XXX	XXX	XXX	Abnormal, NCS	
		Week 12	DDMMMYYYY/xx	XXX	XXX	XXX	Normal	
		Week 24	DDMMMYYYY/xx	XXX	XXX	XXX	Normal	
		Week 36	DDMMMYYYY/xx	XXX	XXX	XXX	Normal	
		Week 40	DDMMMYYYY/xx	XXX	XXX	xxx	Normal	
xxxxxxx	xxxxxxx	Baseline	DDMMMYYYY/xx	xxx	xxx	xxx	Abnormal, CS	xxxxxxxxxxx

Note(s): Day = Day relative to the first day of LTS. NCS = Not clinically significant; CS = Clinically Significant. If a post-baseline finding was determined to be clinically significant, it is also reported as an adverse event. s<nnn>xxxx yyyymmddthh:mm Novan Inc
Protocol Number: NI-AC303

Listing 16.2.7.5
Concomitant Medicati

Listing	16.2.7.5
Concomitant	: Medications
Safety F	opulation

Previous Study	Subject ID	Drug Class/ Preferred Name/ Reported Term	Indication	Start Date (Day)/ End Date (Day)	Dose (Unit) / Frequency / Route	If for AE or MH, Primary Term	Ongoing from Previous Study?
xxxxxx	xxxxxx	XXXXXXXXXXXXXX/ XXXXXXXXXXXXXX/ XXXXXXXX	Adverse Event	DDMMMYYYY (XX)/ Ongoing			
xxxxxxx	xxxxxxx	XXXXXXXXXXXXX/ XXXXXXXXXXXXXXXXXXXXXXX	Medical History	DDMMMYYYY (XX)/ DDMMMYYYY (XX)	XXX.X (XXXXX) / XXX / XXXXXXXXX	XXXXXXXX	Yes
xxxxxx	xxxxxx	XXXXXXXXXXXX/ XXXXXXXXXXXXX/ XXXXXXXXXX	Prophylaxis	DDMMMYYYY (XX)/ DDMMMYYYY (XX)	XXX.X (XXXXX) / XXX / XXXXXXXXX		
xxxxxxx	xxxxxxx	XXXXXXXXXXXX/ XXXXXXXXXXXX/ XXXXXXXXXX	Dietary Supplement	DDMMMYYYY (XX)/ DDMMMYYYY (XX)	XXX.X (XXXXX) / XXX / XXXXXXXXX	XXXXXXXX	No
xxxxxxx	xxxxxxx	XXXXXXXXXXXX/ XXXXXXXXXXXXX/ XXXXXXXXXX	Contraception	DDMMMYYYY (XX)/ DDMMMYYYY (XX)	XXX.X (XXXXX) / XXX / XXXXXXXXX		
xxxxxxx	xxxxxxx	XXXXXXXXXXXXXX/ XXXXXXXXXXXXXXX/ XXXXXXX	Other: XXXXXXXXXXX	DDMMMYYYY (XX)/ DDMMMYYYY (XX)	XXX.X (XXXXX) / XXX / XXXXXXXXX		

Note(s): Day = Day relative to the first day of LTS. Coding will be done using the WHO March 2016 dictionary. Drug Class corresponds to ACT level 2. s<nnn>xxxx yyyymmddthh:mm

Protocol Number: NI-AC303

Listing 16.2.8.1
Adverse Events
Safety Population

Subject ID	Duration of Exposure (days)	Extent of Exposure (grams)	System Organ Class/ Preferred Term/ Reported Term	T E A E	First Dose Date/ Start Date/ End Date / (Days)	Cause Study Discon- tinuation?	Severity / Relationship	Action / Treatment / Final Outcome	SAE?	SAE Criteria
xxxxxx	xx	xx.x	XXXXXXXXXXXXXXX / XXXXXXXXXXXXX / XXXXXXXX	Y	DDMMMYYY / DDMMMYYYY / DDMMMYYYY / XX	No	Mild / Unlikely	Dose Not Changed / XXXXXXXX / XXXXXXXXXXXXXXX	No	
xxxxxx	XX	XX.X	XXXXXXXXXXXXXX / XXXXXXXXXXXXX / XXXXXXXX	Y	DDMMMYYY / DDMMMYYY / DDMMMYYYY / XX	Yes	XXXXXXX / XXXXXXX	XXXXXXXXX / XXXXXXXXX / XXXXXXXXXXXXXXX	Yes	XXXXXXXXX XX

Note(s): TEAE=Treatment-emergent Adverse Event. TEAE onset is based on the start of treatment in the LTS. Days = (Adverse event end date - event start date)+1. Adverse events were coded using MedDRA 18.1. Duration and extent of exposure are based on the date of first dose of study drug, which could from the previous study (NI-AC301 or NI-AC302). s<nnn>xxxx yyyymmddthh:mm

Protocol Number: NI-AC303

Repeat Listing 16.2.8.1 for:

Listing 16.2.8.2 Treatment-Emergent Adverse Events Leading to Discontinuation of Study Drug Safety Population

Listing 16.2.8.3 Treatment-Emergent Adverse Events Leading to Treatment Modification Safety Population

Listing 16.2.8.4 Treatment-Emergent Serious Adverse Events Safety Population

Listing 16.2.8.5 Treatment-Emergent Adverse Events Leading to Death Safety Population

Protocol Number: NI-AC303

Listing 16.2.9 Concomitant Medical and Surgical Procedures Safety Population

Previous Study	Subject ID	Verbatim Term	Start Date (Day) / End Date (Day)	Was it for an AE/SAE?	Ongoing from Previous Study?
xxxxxx	xxxxxx	xxxxxxxxxxxxxxxx	DDMMYYYY (XX) / DDMMYYYY (XX)	No	Yes
xxxxxxx	xxxxxxx	xxxxxxxxxxxxxxxxx	DDMMYYYY (XX) / Ongoing	No	No

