3.4 DOSAGE/DOSE REGIMEN

SB204 will be dispensed from a dual-chamber pump designed to deliver approximately equal amounts of NVN1000 Gel and hydrogel. NVN1000 Gel will be opaque and the hydrogel will be clear. The subject will instantly mix the two substances in the palm of the hand and then immediately massage a thin layer over the acne affected areas once daily after washing. The product should be mixed for about 5 seconds until thoroughly combined with a uniform opaque appearance then applied with the fingertips. Subjects should apply SB204 prior to bedtime.

Up to 2.7 g of SB204 4% will be applied evenly over the acne affected area, including the face, chest, back, and upper shoulders once a day for a period of up to 40 weeks (280 days). The amount of SB204 per application will vary depending on the areas to be treated as shown in Table 1 below. One pump stroke (0.9 g) will be used for the face. Application to the face, upper back and upper chest/shoulders will require up to 2.7 g (three (3) pump strokes).

Table 1: Dosing Amount by Area

Area (BSA)	Number of Pump Strokes	Amount of Product	
Face (3%)	1	0.9 g	
Upper Back (6%)	1	0.9 g	
Upper Chest/Shoulders (8%)	1	0.9 g	

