### 4.4 Extent and Duration of Exposure

Summaries of the duration of exposure, days of exposure, and extent of exposure (calculated total grams) to study drug will be presented, overall and by whether previously randomized to SB204 (SB204 experienced) or randomized to Vehicle (SB204 naïve). This information plus study drug management details will be listed as well. All exposure endpoints will take into account whether the subject received SB204 in the previous study (NI-AC301 or NI-AC302).

Duration of exposure will be defined as:

Date of Last Drug Administration – Date of First Drug Administration + 1 day

Where date of first drug administration is the date of first treatment in the previous pivotal study for subjects randomized to SB204 in the previous study, and date of first dose in the LTS for subjects randomized to vehicle in the previous study.

Days of exposure will be defined as the total number of days that the subject reported taking study medication, and includes the days of exposure to SB204 in the previous study (NI-AC301 or NI-AC302) if applicable.

Extent of exposure will be based on the number of areas treated (face, upper back, and/or upper chest/shoulders, and any other areas reported) and the number of days with treatment. For subjects randomized to SB204 in the previous studies, drug was only applied to the face so for the days of exposure from the previous studies, it will be assumed that there is only one area of application, i.e. the face.

Each application is equal to 0.9 g. Extent of exposure is estimated as the sum of application areas (face only=1, face and chest=2, etc.) times the number of days of application to those areas times 0.9g. For example, a subject who applies 200 applications to the face only will have extent of exposure = 180g, while a subject who applies 100 applications to the face and 50 applications to the upper back will have extent of exposure = 135 g. The maximum extent of exposure would be: [0.9 grams x number of days on treatment in previous study] + [0.9 grams x 4 areas x number of LTS days on treatment]. Most subjects will have less exposure than this, so extent of exposure will be categorized logically depending on actual distribution of subjects. Initially, quartiles will considered.

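### Listing 16.2.6 adds one day to every interval that ends at a re-dispensing, so up to four dates per subject fall in two interval rows

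*SAP*

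**What the plan says.** The note to Listing 16.2.6 gives the duration of an interval as "Date of next drug dispensation or if last dispensataion, date of last dose) - Date of Drug Dispensation + 1 day". The same note derives days from that duration: "Days of Exposure = Duration of exposure minus the number of days that the subject reported not taking study medication". Grams are the number of treated areas times the days of application to those areas times 0.9 g.

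The overall row has its own rule for duration: "Overall is based on the date of first dose of study drug, which could be from the previous study (NI-AC301 or NI-AC302"). For a subject with an unknown interval the note adds: "Overall duration will be defined as above; days of exposure will remain unknown".

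SAP 4.4 defines duration once, over the whole period, as "Date of Last Drug Administration – Date of First Drug Administration + 1 day". It defines days differently from the listing: "Days of exposure will be defined as the total number of days that the subject reported taking study medication", a count that "includes the days of exposure to SB204 in the previous study (NI-AC301 or NI-AC302) if applicable". The note to Table 14.2.1 repeats the reported-days definition.

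On conduct, Protocol 4.1.2 has new drug dispensed, and treated areas recorded, at Weeks 4, 12, 24 and 36 (Days 28, 84, 168, 252). Protocol 3.4 sets one application a day for up to 280 days and says: "Subjects should apply SB204 prior to bedtime".

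**The concern.** Adding 1 to a difference of dates is right when both end dates are dosing dates that belong to the interval. That is so for the whole-period duration in SAP 4.4, and for the last interval in the listing, which ends on the date of last dose. It is not so for an interval that ends at the next dispensing, because that date is also the first date of the next interval. With one application a day, taken at bedtime, the dose on a clinic day belongs to the new interval only.

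Days and calculated grams are the dose measures of a study whose one objective is long-term safety. Gram bands form the columns of Table 14.3.3.2.2 and of the tables built on its shell, and grams stand beside each event in Listing 16.2.8.1. If the interval rows feed those outputs, exposure is slightly overstated, days can exceed duration for the same subject, and a subject near a cut-off can fall in the wrong column.

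**Working it through.** **The plan's own figures.** SAP 4.4 gives two gram examples, and both reproduce: 200 × 0.9 = 180 g, and (100 + 50) × 0.9 = 135 g. The 40-week period is 40 × 7 = 280 days.

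**Inputs.** Dispensing on Days 0, 28, 84, 168 and 252 (schedule of visits). First dose on Day 0, last dose on Day 279 (bedtime before the Week 40 visit), no missed doses (assumptions).

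**Interval rows.**

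| Interval | Listing formula | Possible doses |
|---|---|---|
| Day 0 to 28 | 28 − 0 + 1 = 29 | 28 |
| Day 28 to 84 | 84 − 28 + 1 = 57 | 56 |
| Day 84 to 168 | 168 − 84 + 1 = 85 | 84 |
| Day 168 to 252 | 252 − 168 + 1 = 85 | 84 |
| Day 252 to last dose 279 | 279 − 252 + 1 = 28 | 28 |
| Sum | 284 | 280 |

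The first four rows are one day too high whatever is done with them later; in the Week 4 row this is 1/28 = 3.6%. The last row is correct. SAP 4.4 gives 279 − 0 + 1 = 280, so the sum is 4 days too high (4/280 = 1.4%). With a last dose on Day 280 the figures are 285 against 281, again 4.

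**General form.** With k dispensing dates d1 to dk and last dose date L, the rows sum to (L − d1 + 1) + (k − 1). The excess is k − 1 whatever the visit windows: at most 4 on the planned schedule, none for a subject with a single dispensing, and none from a visit at which no drug is dispensed.

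**Grams, if the rows are summed** (0.9 g per area per day):

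| Areas | Listing | Correct | Excess |
|---|---|---|---|
| 1 | 255.6 | 252.0 | 3.6 |
| 2 | 511.2 | 504.0 | 7.2 |
| 3 | 766.8 | 756.0 | 10.8 |
| 4 | 1022.4 | 1008.0 | 14.4 |

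**Days against duration, if the rows are summed.** A fully adherent SB204-naive subject has 284 days against a duration of 280. For an SB204-experienced subject, assume 84 pivotal dosing days. Summed days are 84 + 284 = 368. Duration is 84 + gap + 280 = 364 + gap, and Protocol 3.5 allows a gap of 0 to 7 days, so duration is 364 to 371. Days exceed duration only if the gap is under 4 days.

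**Gram bands.** The mock tables print cut-offs at 100, 330 and 675 g. An adherent, face-only, experienced subject has 0.9 × 364 = 327.6 g correctly and 0.9 × 368 = 331.2 g from summed rows, so the band changes. The other seven constant-area profiles (1 to 4 areas, naive or experienced, fully adherent) stay in their band. For face-only use with a 4-day excess, a crossing of 330 g needs true days d with 0.9d ≤ 330 < 0.9(d + 4), that is d = 363 to 366.

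**After correction.** 28 + 56 + 84 + 84 + 28 = 280, which equals the SAP 4.4 duration.

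**The case against.** The strongest reply is that the error may never leave the listing.

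- **Roll-up.** No sentence says that overall days are the sum of the rows. If they are overall duration minus missed days, an adherent naive subject shows 280 and 280. The unknown-interval rule does not settle this, because one unknown count of missed doses leaves overall days unknown under either method.
- **Definition.** SAP 4.4 and Table 14.2.1 count days reported taken, not dispensing dates. Diaries are reviewed at each visit, so reported days in an interval could be multiplied by that interval's areas without using the formula at all.
- **Size.** The excess is about 1.4% in a descriptive study, and SAP 4.4 leaves the gram categories to the actual distribution of subjects.

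All three stand as limits on the consequences. None defends the formula: the rows that end at a re-dispensing are wrong under any roll-up. Areas are recorded per visit and can change, so grams are most naturally built interval by interval, and the only written interval rule for days is the one in the listing note. That makes summation the likely reading, but it remains an inference.

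**Conclusion.** The listing formula overcounts by one day in each row that ends at a re-dispensing, at most four rows per subject on the planned schedule. This follows directly from the note and the visit schedule. Baseline and Week 40 are not double counted.

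A reader might infer that exposure in Table 14.2.1 and in the adverse-event tables by grams is therefore inflated, or that adherent subjects in general will show more days than duration. The documents do not establish either. Both need overall days and grams to be summed from the listing rows. Given that, the excess for a fully adherent 40-week subject is 4 days (1.4%), 3.6 g for one area and 10.8 g for three. Days then exceed duration for adherent naive subjects, and for experienced subjects only with a gap under 4 days (84 pivotal days assumed). Few subjects would change band, and the bands are provisional. The severity is minor: a rule that gives a wrong number, small in effect and cheap to correct.

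**What to change.** In the note to Listing 16.2.6:

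1. For every interval that ends at a later dispensing, set interval days to next dispensing date minus dispensing date. Keep the added day only for the last interval, which ends on the date of last dose.
2. State how overall days and grams are formed: from the sum of the intervals, or from a direct count.
3. Align the definition of days with SAP 4.4 and Table 14.2.1 (days reported taken).
4. Add a programming check that interval durations over the long-term study do not exceed the whole period. Either start the first interval at the first dose date in this study, or compare the sum with last dose date minus first dispensing date plus 1. Comparing intervals that start at dispensing with a limit that starts at first dose would fail wrongly whenever the first dose falls after the dispensing date.

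The cost is a few lines in the note and the derivation specification, with no new data. If the outputs would have been built from summed rows, reported exposure for a fully adherent 40-week subject falls by 4 days: from 284 to 280 for a naive subject, about 1.4%. If they are built from diary counts, only the listing changes.

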2. RATIONALE AND OBJECTIVES

2.1 STUDY RATIONALE

Novan is conducting this study to evaluate the long term safety of SB204 4% administered once daily. Subjects will dose once daily for up to 40 weeks (280 days) with SB204 4% to acne affected areas. Based on the previous human safety data with SB204 at up to 8% and Vehicle Gel as well as the nonclinical safety data including dosing with and without hydrogel, this dose is expected to be safe and well tolerated.

[figure not shown]

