3.5 VISIT SCHEDULE

The Week 12 visit for the pivotal studies NI-AC301 or NI-AC302 will serve as the Baseline Visit for this long term safety study. Subjects must have completed the full 12 weeks of treatment in one of the pivotal studies to enroll in the long term safety study. Subjects may enter the long term safety study up to 7 calendar days after their Week 12 visit in the pivotal study. Study visits will take place after the first four weeks then at Weeks 4, 12, 24, 36 and 40.

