3.7.2 INCLUSION CRITERIA

Each subject must fulfill all of the following inclusion criteria to participate in the study:

- 1. Have a signed written informed consent form. Subjects less than 18 years of age or the age of majority in their state must sign an assent form for the study and a parent or a legal guardian must sign the informed consent;
- 2. Have completed the full 12 weeks of treatment in NI-AC301 or NI-AC302;
- 3. Be in good general health;
- 4. Have no more than two nodules or cysts on the face;
- 5. Women of childbearing potential (WOCBP) must have a negative urine pregnancy test (UPT) prior to enrollment;
- 6. WOCBP must agree to use an effective method of birth control during the course of the study and for 30 days after their final study visit;
- 7. Be willing and able to follow study instructions and likely to complete all study requirements. Subjects under 18 years of age or age of majority must be accompanied by the parent or legal guardian at the time of assent/consent signing.

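### Days of exposure is defined in two non-equivalent ways, and the listing version can count the between-study gap, or dispensing dates twice, as dosed days

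*SAP*

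**What the plan says.** SAP 4.4 gives one definition: "Days of exposure will be defined as the total number of days that the subject reported taking study medication". It adds that the count "includes the days of exposure to SB204 in the previous study (NI-AC301 or NI-AC302) if applicable". The note to Table 14.2.1 repeats this definition.

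The note to Listing 16.2.6 gives another: "Days of Exposure = Duration of exposure minus the number of days that the subject reported not taking study medication". Duration in that note is computed per visit interval, from one dispensing date to the next (or to the last dose), plus one day. For the Overall row, "Overall is based on the date of first dose of study drug, which could be from the previous study (NI-AC301 or NI-AC302"). This matches SAP 4.4 on duration, where "date of first drug administration is the date of first treatment in the previous pivotal study for subjects randomized to SB204".

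The same listing note has a rule for undocumented use. If a subject is lost to follow-up, or has not returned the diary and the number of missed doses is not known, the interval is marked UNK and overall days of exposure stay unknown.

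Grams are 0.9 g times the number of areas times the days of application to them. Days from the pivotal study are treated as face only.

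On timing, Protocol 3.5 says: "Subjects may enter the long term safety study up to 7 calendar days after their Week 12 visit in the pivotal study".

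**The concern.** One definition counts days reported as taken. The other counts every calendar day in a span except those reported as missed. They give the same answer only if each day is classified. A day reported neither way is undosed under SAP 4.4 and dosed under the listing note, so outside the UNK rule the listing value can only equal or exceed the SAP 4.4 value. Table 14.2.1 and Listing 16.2.6 would then report the same variable under different rules.

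Long-term safety is the primary objective, so the amount of exposure behind the safety conclusions should not be overstated by a derivation. Grams of exposure also set the columns of Table 14.3.3.2.2 and its repeats, which Protocol 7.7 intends for finding an exposure-related signal. If the listing's day count supplies the grams, a subject can be placed in a higher exposure column without having used more drug.

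**Working it through.** **The plan's own figures.** SAP 4.4 gives two worked examples at 0.9 g per application. 200 × 0.9 = 180 g, and (100 + 50) × 0.9 = 135 g. Both reproduce.

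**Inputs.**
- Pivotal treatment: 12 weeks = 84 days (Protocol 3.7.2: "Have completed the full 12 weeks of treatment in NI-AC301 or NI-AC302").
- Long-term study: up to 280 days (Protocol 2.1: "Subjects will dose once daily for up to 40 weeks (280 days) with SB204 4% to acne affected areas").
- Gap between studies: 0 to 7 days (Protocol 3.5).
- Category boundary: 330 g (Table 14.2.1 shell).

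**The two definitions.**
- SAP 4.4: days = days reported taken.
- Listing note: days = (last − first + 1) − days reported not taken.
- Difference: days reported neither way. On the Overall row this includes the gap for experienced subjects, unless gap days are reported as not taken.

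**Overall row read literally** (fully adherent, face only, SB204-experienced).
- SAP 4.4: 84 + 280 = 364 days; 364 × 0.9 = 327.6 g, in the category above 100 to 330 g.
- Listing with a 7-day gap: 84 + 7 + 280 = 371 days; 371 × 0.9 = 333.9 g, in the category above 330 to 675 g. Excess: 7 days, 6.3 g, 7/364 = 1.9%.
- A 3-day gap is enough to cross: 367 × 0.9 = 330.3 g.
- If gap days were multiplied by four areas, the excess is 7 × 4 × 0.9 = 25.2 g.
- If Week 40 is timed from the pivotal Week 12 visit, the gap uses up long-term time: SAP 4.4 gives 357 days (321.3 g), the listing 364 days (327.6 g). Excess 7/357 = 2.0%, with no change of category.
- For SB204-naïve subjects the gap effect is zero, because their span starts in the long-term study.

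**Summing the visit intervals instead.** This avoids the gap, but the one-day addition in every interval counts each intermediate dispensing date (Weeks 4, 12, 24 and 36) in two intervals.
- With dosing from Day 0 to Day 279 and on-schedule visits: (28 + 1) + (56 + 1) + (84 + 1) + (84 + 1) + (279 − 252 + 1) = 29 + 57 + 85 + 85 + 28 = 284 days, against 280.
- Excess: 4 days, 3.6 g face only, in both experienced and naïve subjects.
- For the adherent face-only experienced subject: 84 + 284 = 368 days; 368 × 0.9 = 331.2 g, again across 330 g.

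**Blank days in a returned diary.** Each such day adds 0.9 g per area treated under the listing rule if it feeds grams. The documents give no share. As an assumption only, 5% to 30% of 280 days is 14 to 84 days, or 12.6 to 75.6 g face only and 50.4 to 302.4 g for four areas on every such day. Days under the UNK rule add nothing.

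**Does the day count feed grams?** The formula refers to days of application and does not name the listing's subtraction as its source. Two things point that way. The pivotal part of grams is computed from days of exposure in the earlier study. In the Listing 16.2.6 shell, grams are UNK at Week 36 and on the Overall row, exactly where days are UNK, although overall duration is known.

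**The case against.** The strongest reply is that the two wordings may be one rule. The UNK rule speaks of missed doses, which suggests that missed doses are what is collected. Subtraction would then simply be how days taken are obtained. The diary format is not in the documents, and sites review diary completion and compliance at every post-baseline visit. This stands as a limit on the blank-day part: how many days are unclassified is unknown and may be few. It does not remove the gap or the repeated dispensing dates, which come from the formula.

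It can also be said that the sentence about the Overall row concerns duration, and that SAP 4.4 reads as adding pivotal days to long-term days. That is a sensible reading and is the one to adopt. But the listing note defines days from duration and states no exception for the Overall row, so a programmer following it would include the gap.

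A reader might infer more than this, and the documents do not support it:
- That undocumented days in general count as dosed. The UNK rule covers a large part of them, and Table 14.2.1 has rows for unknown days and grams.
- That treatment pauses during remission inflate the count. They are subtracted if reported as not taken.
- That days of exposure define the adverse-event categories. Only grams do. The time windows use duration since first SB204 dose.
- That grams are shown to be inflated. This follows only if the listing count supplies them.

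Two further points stand. The gram cut-points are provisional, since SAP 4.4 leaves categories to the observed distribution. Counting only documented days can also err, by understating exposure, so a bound on the other side is needed.

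**Conclusion.** Wrong as written, minor in size. One variable has two definitions that are not equivalent, and neither literal use of the listing formula recovers the SAP 4.4 count. The Overall span adds up to 7 days (about 2%, 6.3 g face only) for experienced subjects. The sum of intervals adds 4 days (284 against 280) for a subject who attends every visit.

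A change of category near 330 g rests on three assumptions: the listing count feeds grams, the provisional cut-points are kept, and, for the gap, the 280 days run from entry to the long-term study and not from the pivotal Week 12 visit. The contribution of blank diary days cannot be sized from the documents. A claim of large or general inflation of exposure is not established.

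**What to change.** - Use the SAP 4.4 definition, days reported as taken, in the text, the Table 14.2.1 note and the Listing 16.2.6 note.
- Derive overall days as pivotal SB204 days plus long-term study days, so that the gap is excluded.
- Remove the per-interval double count, for example by ending each interval on the day before the next dispensing date.
- State that this same day count feeds grams.
- Show diary days reported neither as taken nor as missed in their own column, and give the value with all of them counted as taken as an upper bound. Keep the UNK rule as it stands.

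The cost is a revised note and one derivation, with no new data collection. Exposure totals become slightly smaller.
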